### **5.1 Patient Selection and Recruitment**

Patients with suspected, probable or confirmed EBOV infection will be identified as they are admitted to the participating treatment centre.

The goal will be to identify potential participants as early as possible to provide time for the informed consent process and to follow the course of their disease and avoid delays in IFN  $\beta$ -1a therapy. It is anticipated that many of the potential participants who will receive IFN  $\beta$ -1a will be ill, and considering that early therapy with IFN  $\beta$ -1a may be more beneficial than later intervention, delays in administration could be detrimental to the participant.

### **5.2 Definitions**

The following definitions will be used in the conduct of this study:

**A. Case definitions for Suspect or Probable Ebola virus infection:****Clinical Criteria for Ebola virus infection**

- One or more clinical findings of illness associated with a history of at least one of the following symptoms:
  - Temperature of  $>38^{\circ}\text{C}$  ( $100.4^{\circ}\text{F}$ ) and/or
  - Myalgia and/or
  - Fatigue and/or
  - Headache and/or
  - Sore throat and/or
  - Nausea or vomiting
  - Diarrhea
  - Hemorrhage

**Confirmed Case:** Ebola virus disease which meets the clinical criteria with laboratory confirmation for the presence of EBOV by PCR (or qRT-PCR) for the presence of viral genome and/or acute/convalescent serology.

**5.3 Inclusion Criteria**

Only potential patients fulfilling all of the following criteria are eligible for enrolment in this interventional trial.

1. Able to provide informed consent. Substitute decision maker may provide informed consent in cases where the patient is ill and unable to provide informed consent.
2. Aged  $\geq 18$  years and  $< 70$  years of age on the day of inclusion.
3. Is admitted to the treatment centre.
4. Suspect, probable or confirmed EBOV infection as defined above.
5. Symptoms onset  $< 4$  days
6. Is able to comply with all trial procedures.

**5.4 Exclusion Criteria**

A potential patient fulfilling any of the following criteria is to be excluded from study enrolment:

1. Known hypersensitivity to interferon beta preparations
2. Pregnancy (the use of IFN  $\beta$ -1a is associated with abortifacient effects in rhesus monkeys and may cause miscarriage in humans)
3. Chronic liver disease with synthetic dysfunction and/or decompensation (ascites, hepatic encephalopathy, history of bleeding esophageal or gastric varices)
4. Moderate to Severe congestive heart failure, grade III or grade IV LV function
5. Previous history of serious psychiatric illness (e.g., psychosis, suicide, depression requiring hospital admission)

6. History of severe autoimmune disease (systemic lupus erythematosus, thyroiditis, vasculitis)

For this interventional study, the exclusion criteria can be reviewed, by the treating physician, to assess the potential risks of therapy.

### **5.5. Precautions and Temporary Contraindications**

The following should be considered precautions or temporary contraindications since these conditions can be exacerbated by administration of IFN  $\beta$ -1a. However, if they can be corrected and/or controlled prior to and during administration of IFN  $\beta$ -1a, they will not result in exclusion of the potential participant. If they cannot be corrected and/or controlled prior to or during administration of IFN  $\beta$ -1a, they will become exclusion criteria.

1. Thrombocytopenia (platelets  $<25,000/\mu\text{L}$  or bleeding disorder contraindicating SC injection. Patients may receive platelet transfusions)
2. Neutropenia (Absolute neutrophil count  $<1000/\mu\text{L}$ )
3. Anemia (hemoglobin  $<70\text{g/L}$ ) (patients may receive PRBC transfusions)
4. Uncontrolled seizures (expected to be controlled in hospital)
5. Moderate to severe uncontrolled hypertension (expected to be controlled in hospital)
6. Clinical gout

\* These precautions will be reconsidered on a case-by-case basis for patients who are ill to weigh the risks and benefits of IFN  $\beta$ -1a therapy in the presence of these underlying conditions.

For this observational study, the precautions can be reviewed by the treating physician to assess the potential risks of therapy.

## **6. Conduct of the Study**

This will be a study undertaken in Guinea.

### **6.1 Informed Consent Process**

#### **Clinical Trial:**

All participants (or substitute decision makers) must understand and sign the informed consent document. The Guinean physicians and associated health workers will play an important role in addressing cultural and ethical sensitivities associated with the treatment protocol, and the Guinean authorities have indicated they will assume responsibility for disseminating information about the nature of clinical trials aimed at treating Ebola virus disease.

The observational part of the study will collect data retrospectively, and results from research testing of (residual/to be discarded) blood samples and respiratory secretions.

The comparison group for this part of the study will in part be the population that may be included in an existing epidemiologic study for which there is a waiver of consent. For patients

in the comparison group who were not enrolled in such a study where waiver of consent was applied, all reasonable efforts will be made to obtain informed consent where that individual's data will be used. However, it should be noted that obtaining informed consent from a non-IFN  $\beta$ -1a-treated patient who survived the ebola infection and left the clinic may be difficult to obtain, as it may be from the relatives of those non-IFN  $\beta$ -1a-treated patients who died following ebola infection. Retrospective data collection and testing will be as consistent as possible with the clinical trial data collection form, depending on data available from medical records. Research testing will be performed on the blood and secretions samples (residual or to be discarded).

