### **5. Study Design**

This study is single-arm clinical trial with a pre- and post- study design. The study will include patients who are admitted with EBOV infection to a treatment centre. If a patient meets the inclusion criteria and gives informed consent (or informed consent is given by a substitute decision maker who is responsible for the patient due to the patient's illness), the patient will be enrolled into the study i.e. the first 30-50 eligible patients will be enrolled. Patients who receive IFN  $\beta$ -1a will be treated through the Special Access/Compassionate Release Program (consent to treatment through their treating physician) administered in Conakry, Guinea. This part of the study will collect data retrospectively, including results from research testing of (residual/to be discarded) blood samples. The study team can make available the systematic data collection forms to the treating physician to help in monitoring of adverse events and effect of therapy, enabling more specific reporting to the Special Access Program administered in Conakry, Guinea by the treating physician for patients receiving IFN  $\beta$ -1a.

As noted above, retrospective data collection will include patients with EBOV disease who do not participate in this clinical trial. Data from IFN  $\beta$ -1a-treated patients will be matched with data from patients who did not receive IFN  $\beta$ -1a, based on age, sex, estimated days post-onset of symptoms, and viral load (if available). This data collection is similar to that proposed in this protocol. Also, this protocol proposes to test blood collected clinically (residual or to be discarded) for comparisons between the groups in this interventional study.

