### **6.2 Initial Evaluation and Baseline Investigations:**

Once the informed consent is signed, and prior to initiation of therapy, eligibility will be confirmed. Some of the data (e.g. demographics) may be collected retrospectively from the patients' chart (source document). Demographics will be collected, the participant will undergo evaluation to review the medical history (will be recorded from the chart and/or obtained from the participant or family members) and a physical examination will be performed by a study physician or one of the treating physicians (chart). These will be recorded in the case report form. The patient's current clinical status will also be documented.

Pre-study screening and baseline investigations will occur, preferably on the same day as signature of the Informed Consent, but definitely prior to initiation of treatment with IFN  $\beta$ -1a, and will be stated as performed on day 1 of hospitalization and day 'X' of illness. Follow-up data will also be recorded on this basis for comparison between relevant time points amongst participants (treated or not with IFN  $\beta$ -1a). It is expected that most eligible participants will be treated within 24 hours of being admitted to the treatment centre. Earlier therapy with IFN  $\beta$ -1a in the course of disease of the illness is likely to offer the highest chance of potential benefits to prevent further deterioration. Days 1-10 mentioned with each of the investigations noted below refer to the days of IFN  $\beta$ -1a therapy and/or follow-up while in hospital. Patients discharged prior to 10 days from initiation of therapy will, if possible, be seen for medical and study follow-up at 1 month post-initiation of treatment. Every effort will be made to combine clinical care follow-up with study follow-up.

Data available in the medical chart will be collected.

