### 9.3 Tertiary

**Clinical:** Clinical improvement: will be evaluated by comparing the following parameters between the groups:

- Incidence of fever ( $>38^{\circ}\text{C}$ ), persistence, and duration.
- Incidence and duration of other symptoms of illness: chills, myalgia, sore throat, cough, nausea, vomiting, diarrhea, and hemorrhage.
- Death – all causes for study duration

Monitoring the clinical course consistently as opposed to looking at the effect of IFN  $\beta$ -1a on a case-by-case basis should provide additional information to guide indications for therapy during the epidemic and provide detailed surveillance data during this public health emergency.

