## 10.2 Statistical analyses and methods

Demographics, and underlying conditions will be described by means and standard deviation for continuous variables, by median and interquartile range for ordinal or count variables, and by frequencies and percentages for categorical variables. Endpoints will be described and compared between treatment and usual standard of care groups using cross-tabulation tables and Fisher's Exact test for categorical variables, t-test for normally distributed continuous variables and Wilcoxon non-parametric test for non-normally distributed continuous or ordinal variables.

Safety variables such as fever will be considered in three different formats:

1. As ordinal, representing various levels of severity of the symptom. For instance, fever will be described as "none", "mild", "moderate", or "severe".
2. As binary, considering only the presence vs. the absence of the symptom.
3. As binary, considering the most serious expression of the symptom. For instance by grouping "moderate" and "severe" together.

Separate analyses for time periods of 0-3, 4-7, and 8-10 days will be conducted. For each of these time periods the most severe report of the AE for each participant will be counted.

Adverse Events and Serious Adverse Events will be considered in two ways: presence of any event and presence of any event related to the treatment.

Symptoms will be assessed as a repeated measure using GEE modelling.

Survival will be analyzed using a Kaplan-Meier curve and Cox-proportional hazard modeling with 2 week and 1 month survival rates determined.

Viral clearance will be analyzed as binary variables for detection (presence) or non-detection (absence) as well as continuous variables where applicable (e.g. quantitative RT-PCR measurements).

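### Part of the comparison group is assembled through consent from discharged survivors or relatives of the dead, with no rule for failed consent, so comparator mortality may depend on who is reached

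*Protocol*

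**What the plan says.** **Sources of comparators.** Protocol section 5 states that "retrospective data collection will include patients with EBOV disease who do not participate in this clinical trial". Section 6.1 gives two sources. First, "The comparison group for this part of the study will in part be the population that may be included in an existing epidemiologic study" that runs under a waiver of consent. Second, for comparators outside that study, "all reasonable efforts will be made to obtain informed consent where that individual's data will be used". The next sentence concedes that consent from an untreated patient "who survived the ebola infection and left the clinic may be difficult to obtain, as it may be from the relatives of those" who died. The share expected from each source is not given.

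**Treated patients.** Section 6.2: "Once the informed consent is signed, and prior to initiation of therapy, eligibility will be confirmed". Patients given interferon therefore enter before their outcome is known.

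**Matching.** Section 5 matches on age, sex, estimated time since symptom onset and, where it exists, viral load.

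**Use of the comparison.** Section 9.3 lists "Death – all causes for study duration" among the parameters compared between the groups. Section 10.2 adds: "Survival will be analyzed using a Kaplan-Meier curve and Cox-proportional hazard modeling with 2 week and 1 month survival rates determined". It also compares endpoints generally between the treated and usual-care groups. Section 16 makes safety and, if the small sample allows, a trend in efficacy against standard of care the factors that decide whether to extend to 100 participants and whether a larger study is appropriate.

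**The concern.** Outside the waiver population, the person asked for consent is set by the patient's outcome: the survivor, or the relatives of someone who died. These are two different routes with two possibly different success rates. If patients whose consent is not obtained are dropped, the comparison group is partly selected on the outcome that is then compared, while the treated group is not assembled in that way.

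Matching balances characteristics present at admission. It does nothing about selection on vital status among patients who share those characteristics. If families of the dead are harder to reach, comparator mortality is understated and interferon looks worse. If discharged survivors are harder to reach, comparator mortality is overstated and interferon looks better. Either error would feed the efficacy trend that helps to decide on extension.

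**Working it through.** The protocol gives no consent rate, comparator number, waiver share or effect size, so there is no figure of its own to reproduce. What follows is an illustration that **assumes patients without consent are left out**.

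**Inputs from the protocol**
- Fatality p: 57% to 90% (section 1.1). Guinea's crude ratio from the table in section 1.2 is 1214/2047 = 59.3%.
- Treated patients: 30 to 50 (section 10.1).

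**Assumed inputs**
- Consent rate s among survivors and d among families of the dead.
- Share w of the included comparators that comes from the waiver source, taken to show the true fatality.

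**Formulas**
- Observed fatality in the consented source: O = p·d / [p·d + (1 − p)·s]
- Pooled comparator fatality: w·p + (1 − w)·O

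**Results at p = 0.57**
- s = 0.8, d = 0.4: 0.228 / (0.228 + 0.344) = 0.228/0.572 = 39.9%, about 17 points low.
- s = 0.4, d = 0.8: 0.456 / (0.456 + 0.172) = 0.456/0.628 = 72.6%, about 16 points high.
- s = 0.7, d = 0.5: 0.285/0.586 = 48.6%. The reverse: 0.399/0.614 = 65.0%.
- w = 0.5 with the 80%/40% rates: (57.0 + 39.9)/2 = 48.4%. The reverse: (57.0 + 72.6)/2 = 64.8%.
- s = d: 57.0%, no shift.

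Here w = 0.5 means half of the comparators actually included. If instead half of the eligible pool, before consent losses, lies under the waiver, the figures are 0.399/0.786 = 50.8% and 0.513/0.814 = 63.0%.

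**Other fatality levels, twofold consent ratio**
- p = 59.3%: 42.2% and 74.5% at w = 0; 50.7% and 66.9% at w = 0.5.
- p = 90%: 81.8% and 94.7% at w = 0.

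**Chance of a false mortality difference.** This takes no true effect, p = 59.3%, a twofold consent ratio in either direction, equal groups and a two-sided Fisher test at 0.05. Comparator number and test level are assumptions, and the test is a simple stand-in for the planned survival analysis.

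| Per group | Equal consent | w = 0 | w = 0.5 |
|---|---|---|---|
| 30 | 2.6% | 16.2% to 19.1% | 5.4% to 6.3% |
| 50 | 3.2% | 28.9% to 35.0% | 8.6% to 10.6% |

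**The case against.** The strongest reply is that section 6.1 promises effort and does not state an inclusion rule. A reader might infer that comparators outside the waiver study enter only with consent, and only once their outcome is known. The text says neither. It speaks of people whose data will be used and then warns that consent may not be obtained, which can be read to mean that the charts are used regardless. In that case nobody is selected on outcome through this route. Nor does it rule out asking untreated patients while they are still admitted; section 6.2 mentions follow-up of participants whether treated or not. This stands: exclusion and late consent are natural inferences from a retrospective design and from the two groups named, but they are not stated rules.

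Three further points stand:
- The protocol calls both routes difficult and does not say which is harder. Direction is therefore unknown, and the twofold ratios are assumptions.
- With no effect size anywhere in the protocol, one cannot say that the shift would exceed a plausible treatment effect.
- That the waiver population was itself assembled without regard to outcome is not documented.

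The reach is also limited. Death is a tertiary endpoint in a feasibility pilot described as single-arm, and the synopsis comparison of baseline with day 10 within treated patients is untouched. Treated patients' data may also be incomplete, and they may withdraw.

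What does not stand is that this is only missing detail. The protocol foresees failed consent along routes set by vital status, pools the two sources without distinction, and uses the result in a between-group survival comparison. An analysis plan cannot later recover patients who were never included.

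**Conclusion.** The point holds in a conditional form. The firm defect is that section 6.1 anticipates unobtainable consent without saying whether those patients are left out, and that nothing in the protocol separates the consented comparators from the waiver population. If they are left out, comparator mortality can depend on who was reached, and the planned matching cannot correct it.

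Size rests on assumed consent rates. At 57% fatality and a twofold ratio, the consented source would show 39.9% or 72.6%, and the pooled group 48.4% or 64.8% if half of the included comparators come from an unbiased waiver source. The shift is nil if consent rates are equal or the data are used anyway, and it shrinks as the waiver share grows. It would be wrong to conclude that the comparison is biased in a known direction or by a known amount. The between-group viral and safety comparisons use the same comparators, but no size has been worked out for them. The change should be made before the comparison group is assembled.

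**What to change.** In sections 5 and 6.1, state that the main between-group comparison uses only comparators whose inclusion does not depend on outcome. Two sources could serve:
- all qualifying patients in the waiver population, after confirming that enrolment in that epidemiologic study did not depend on outcome; or
- all qualifying charts, if the ethics committees of the participating centres extend the waiver to them.

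Comparators added through consent sought after the event go into a sensitivity analysis only. Report the numbers sought and included by vital status and by source, so that a reader can see whether inclusion differed between survivors and the dead.

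The cost is protocol wording plus a waiver request to each centre's committee, since section 14 requires review for each treatment centre. If the waiver is not extended, the main comparator pool will be smaller, and matching on time since onset and viral load may be harder to achieve.

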### **6.2 Initial Evaluation and Baseline Investigations:**

Once the informed consent is signed, and prior to initiation of therapy, eligibility will be confirmed. Some of the data (e.g. demographics) may be collected retrospectively from the patients' chart (source document). Demographics will be collected, the participant will undergo evaluation to review the medical history (will be recorded from the chart and/or obtained from the participant or family members) and a physical examination will be performed by a study physician or one of the treating physicians (chart). These will be recorded in the case report form. The patient's current clinical status will also be documented.

Pre-study screening and baseline investigations will occur, preferably on the same day as signature of the Informed Consent, but definitely prior to initiation of treatment with IFN  $\beta$ -1a, and will be stated as performed on day 1 of hospitalization and day 'X' of illness. Follow-up data will also be recorded on this basis for comparison between relevant time points amongst participants (treated or not with IFN  $\beta$ -1a). It is expected that most eligible participants will be treated within 24 hours of being admitted to the treatment centre. Earlier therapy with IFN  $\beta$ -1a in the course of disease of the illness is likely to offer the highest chance of potential benefits to prevent further deterioration. Days 1-10 mentioned with each of the investigations noted below refer to the days of IFN  $\beta$ -1a therapy and/or follow-up while in hospital. Patients discharged prior to 10 days from initiation of therapy will, if possible, be seen for medical and study follow-up at 1 month post-initiation of treatment. Every effort will be made to combine clinical care follow-up with study follow-up.

Data available in the medical chart will be collected.

### **Baseline Investigations:**

Given that this is an outbreak with limited health care resources available at the different treatment centres, baseline investigations will be resource-dependent and may include

- Fever/temperature measurement
- PCR determination of viremia
- Clinical evaluation of severity of symptoms such as chills, myalgia, sore throat, cough, nausea, diarrhea, hemorrhage

### 6.3 Treatment Schedule

IFN  $\beta$ -1a will be obtained from BiogenIdec Inc., Cambridge, MA 02142, USA. The dosage will be as follows: 6 million IU SC  $\times$  10 days. Administration should follow the product monograph, and will generally be done by the patient's nurse while in the treatment centre.

The IFN  $\beta$ -1a dose may be decreased if there are problems with tolerance by 3 million IU (15  $\mu$ g) to 3 million IU. Once it is well tolerated, the dose may remain the same or may be re-increased by 3 million IU to a maximum of 6 million IU/30  $\mu$ g per day. Dose adjustments are under the treating physician responsibility.

The duration of treatment may be shorter than 10 days in cases where the patient recovers more rapidly, with a minimum of 7 days therapy. The decision to stop IFN  $\beta$ -1a therapy in such cases will be made by the patient's treating physician. In general, patients are expected to discontinue treatment upon discharge from the treatment centre or about 48 hours prior to discharge for observation of deterioration of treatment. Most patients are expected to be admitted at least 7 days due to the nature of the illness. If any patient needs to discontinue prior to day 7 of therapy, the rationale will be documented on a case-by-case basis.

